In view of the COVID-19 pandemic, alternative arrangements to conduct study visits according to the protocol may be considered.

- ^a Screening and signing of the informed consent form (ICF) will occur at baseline (Day 1), which is also the day of Dose 1 vaccination. If needed, the screening activities may be split over multiple visits, with a maximum time of up to 28 days between signing the ICF and Dose 1 vaccination.
- ^b In addition to the assessments scheduled during the study site visits, participants will be instructed to contact the investigator before the next visit if they experience any adverse event or intercurrent illness that they perceive as relevant and/or can be possibly related to study vaccine in their opinion.
- ^c Signing of the ICF needs to be done before the first study-related activity.
- ^d The investigator should ensure that all study enrollment criteria have been met at the end of screening. If a participant's clinical status changes (including receipt of additional medical records) after screening but before Dose 1 vaccination such that he/she no longer meets all eligibility criteria, then the participant should be excluded from further participation in the study.

- ^e Prestudy-specific therapies such as analgesic/antipyretic medications, nonsteroidal anti-inflammatory drugs, vaccines, and immunomodulators/suppressors (eg, cancer chemotherapeutic agents, systemic corticosteroids) administered up to 30 days prior to Dose 1 vaccination and previous vaccinia/smallpox vaccination at any time prior to study entry must be recorded in the electronic case report form (eCRF).
- ^f The investigator must check for acute illness or body temperature $\geq 38.0^{\circ}\text{C}$ at the time of vaccination. In such cases, the participant may be vaccinated up to, and no later than 10 days after the scheduled vaccination, or be withdrawn at the discretion of the investigator and after consultation with the sponsor.
- ^g Prior to study vaccine administration.
- ^h For women of childbearing potential.
- ⁱ A full physical examination (excluding genito-urinary system), including height and body weight, will be carried out at screening (Day 1). At other visits, an abbreviated, symptom-directed examination will be performed as indicated by the investigator.
- ^j Includes blood pressure and pulse/heart rate (at least 5 minutes of rest in supine position), and oral temperature.
- ^k Participants will receive a diary to document symptoms of solicited local and systemic adverse events (reactogenicity). At Day 1, in addition to the diary, a ruler and thermometer will be distributed to each participant.
- ^l The participants will complete diary cards until 7 days post each vaccination (solicited adverse events), which will be reviewed by study site personnel at the Day 57 visit (before Dose 2 vaccination) and at the Day 78 visit.
- ^m After each vaccination, participants will remain under observation at the study site for at least 30 minutes for presence of any acute reactions or solicited events. Solicited and unsolicited adverse events emerging during the observation period will be recorded in the eCRF.
- ⁿ Solicited adverse events will be documented in the evening after each vaccination and then daily for the next 7 days.
- ^o All adverse events and special reporting situations, whether serious or nonserious, that are related to study-related procedures or to non-investigational (concomitant) sponsor products, and pregnancy (if applicable), will be reported from the time a signed and dated ICF is obtained onwards. Other serious adverse events and special reporting situations will be reported from first dose of study vaccine until the end of the study. Other nonserious adverse events and special reporting situations will be reported from first dose of study vaccine until 28 days after first dose of study vaccine, and from the second dose of study vaccine until 28 days thereafter. Unsolicited adverse events with the onset date outside the time frame defined above (>28 days after previous study vaccination), which are ongoing on the day of the subsequent vaccination, should be recorded on the eCRF Adverse Event page.
- ^p Participants will be asked about the occurrence of unsolicited adverse events at the Day 57 visit (before Dose 2 vaccination), at the Day 78 visit, and by means of a telephone call at Days 29 and 85.
- ^q Concomitant therapies such as analgesic/antipyretic medications, nonsteroidal anti-inflammatory drugs, vaccines, and immunomodulators/suppressors (eg, cancer chemotherapeutic agents, systemic corticosteroids) must be recorded from Dose 1 vaccination up to 28 days post Dose 1 vaccination and from Dose 2 vaccination up to 28 days post Dose 2 vaccination. All other concomitant therapies should also be recorded beyond these time frames until the end of the study (ie, 6 months post Dose 2) if administered in conjunction with serious adverse events and pregnancies (if applicable).
- ^r This is not required for participants in Groups 5-6 (Booster Cohort).
- ^s Humoral immunogenicity assessments on Days 1, 57, and 78; determination of neutralizing antibodies against the Ad26 vector on Day 1 for Groups 5-6 (Booster Cohort) only.
- ^t Informed consent for Groups 5-6 (Booster Cohort) includes additional procedures. See below.
- ^u Lower limit: Day 57-3 days, upper limit: Day 57+28 days

Additional Visits for Groups 5-6	Booster	Vaccination and Postvaccination Visits ^a				Follow-up	
	Day 177 ±1w	Day 184 ±2d	Day 198 ±3d	Day 205 (Telephone call for safety follow-up) ±1w	Day 357 ±2w	Day 537 ±4w	
Study Procedures	Booster Dose 4 months post Dose 2	7 days post booster dose	21 days post booster dose	28 days post booster dose	6 months post booster dose	12 months post booster dose	
Screening/Administrative							
Prevaccination symptoms ^b	X						
Study vaccine administration	▲						
Immunogenicity Assessments							
Blood sampling for immunogenicity assays (8.5 mL per blood draw) ^c	X ^d	X	X		X	X	
Safety Assessments							
Urine pregnancy test ^e	X ^d						
Physical examination ^f	X ^d	X ^f	X ^f				
Vital signs ^g	X ^d	X ^g	X ^g				
Distribution of participant diary ^h	X						
Review of participant diary by study site personnel ⁱ		X					
30-minute postvaccination observation ^j	X						
Solicited adverse events recording ^k	From booster vaccination until 7 days post booster						
Unsolicited adverse events recording ^{l,m}	From booster vaccination until 28 days post booster						
Pregnancy, serious adverse events ^l	Continuous						
Concomitant medications ⁿ	From booster vaccination until 28 days post booster				X ⁿ		

▲ Ad26.ZEBOV 5x10¹⁰ vp

d: days; w: week

^a In addition to the assessments scheduled during the study site visits, participants will be instructed to contact the investigator before the next visit if they experience any adverse event or intercurrent illness that they perceive as relevant and/or can be possibly related to study vaccine in their opinion.

^b The investigator must check for acute illness or body temperature $\geq 38.0^{\circ}\text{C}$ at the time of vaccination. In such cases, the participant may be vaccinated up to, and no later than 10 days after the scheduled vaccination or be withdrawn at the discretion of the investigator and after consultation with the sponsor.

^c Humoral immunogenicity assessments on Days 177, 184, 198, 357 and 537; assessment of neutralizing antibodies against the Ad26 vector on Days 177 and 198.

^d Prior to study vaccine administration.

^e For women of childbearing potential.

- f An abbreviated, symptom-directed examination will be performed as indicated by the investigator.
- g Includes blood pressure and pulse/heart rate (at least 5 minutes of rest in supine position), and oral temperature.
- h Participants will receive a diary to document symptoms of solicited local and systemic adverse events (reactogenicity).
- i The participants will complete diary cards until 7 days post each vaccination (solicited adverse events), which will be reviewed by study site personnel at the Day 184 visit.
- j After each vaccination, participants will remain under observation at the study site for at least 30 minutes for presence of any acute reactions or solicited events. Solicited and unsolicited adverse events emerging during the observation period will be recorded in the eCRF.
- k Solicited adverse events will be documented in the evening after each vaccination and then daily for the next 7 days.
- l All adverse events and special reporting situations, whether serious or nonserious, that are related to study-related procedures or to non-investigational (concomitant) sponsor products, and pregnancy (if applicable), will be reported from the time a signed and dated ICF is obtained onwards. Other serious adverse events and special reporting situations will be reported from first dose of study vaccine until the end of the study. Other nonserious adverse events and special reporting situations will be reported from first dose of study vaccine until 28 days after booster dose of study vaccine.
- m Participants will be asked about the occurrence of unsolicited adverse events at the Day 177 visit (before booster dose vaccination), Day 184 and Day 198 visits and by means of a telephone call at Day 205.
- n Concomitant therapies such as analgesic/antipyretic medications, nonsteroidal anti-inflammatory drugs, vaccines, and immunomodulators/suppressors (eg, cancer chemotherapeutic agents, systemic corticosteroids) must be recorded from booster dose vaccination up to 28 days post booster dose vaccination. All other concomitant therapies should also be recorded beyond these time frames until the end of the study if administered in conjunction with serious adverse events and pregnancies (if applicable).

ABBREVIATIONS

Ad26	Adenovirus serotype 26
Ad26.ZEBOV	Adenovirus serotype 26 encoding the Ebola virus Mayinga glycoprotein
β-hCG	β-human chorionic gonadotropin
BN	Bavarian Nordic
CI	confidence interval
COVID-19	coronavirus disease 2019
EBOV	Ebola virus
eCRF	electronic case report form
eDC	electronic data capture
ELISA	enzyme-linked immunosorbent assay
EU/ml	ELISA unit/ml
EVD	Ebola virus disease
GCP	Good Clinical Practice
GMC	geometric mean concentration
GMP	Good Manufacturing Practice
GP	glycoprotein
HIV	human immunodeficiency virus
IB	Investigator's Brochure
ICF	informed consent form
ICH	International Council for Harmonisation of Technical Requirements for Pharmaceuticals for Human Use
IDT	IDT Biologika GmbH in Dessau-Rosslau, Germany
IEC	Independent Ethics Committee
IM	intramuscular(ly)
Inf U	infectious unit(s)
IRB	Institutional Review Board
IUD	intrauterine device
IUS	intrauterine hormone-releasing system
IWRS	interactive web response system
kb	kilobase
MARV	Marburg virus
MedDRA	Medical Dictionary for Regulatory Activities
MVA	Modified Vaccinia Ankara
MVA-BN-Filo	Modified Vaccinia Ankara Bavarian Nordic vector expressing multiple filovirus proteins
NHP	nonhuman primate(s)
NP	nucleoprotein
PCR	polymerase chain reaction
PQC	Product Quality Complaint
PREVAC	Partnership for Research on Ebola Vaccination
SAP	Statistical Analysis Plan
SARS-CoV-2	severe acute respiratory syndrome coronavirus 2
SMT	Safety Management Team
SUDV	Sudan virus
SUSAR	suspected unexpected serious adverse reaction
TAFV	Tai Forest virus
VISP	vaccine-induced seropositivity
vp	viral particle(s)
vs	versus
WHO	World Health Organization

DEFINITIONS OF TERMS

Study vaccine	Ad26.ZEBOV, MVA-BN-Filo, or placebo
Independent study vaccine monitor	An unblinded study vaccine monitor assigned to the study who is responsible for the unblinded interface between the sponsor and the study site pharmacy.
Solicited adverse events (reactogenicity)	Local (at injection site) and systemic adverse events that are common and known to occur after vaccination and that are usually collected in a standard, systematic format in vaccine clinical studies. For the list of solicited adverse events in this study, see Section 9.3. For the purpose of vaccine clinical studies, all other adverse events are considered unsolicited; however, this definition should be distinguished from definitions based on pharmacovigilance guidelines.
Immunogenicity subset	A subset of 456 participants in Groups 1-4 (144 in each of Groups 1 to 3 and 24 in Group 4) that will be assessed for immunogenicity.

Study Naming Convention

Clinical studies with the Ad26.ZEBOV and MVA-BN-Filo vaccines are referred to as study VAC52150EBLXXXX (eg, study VAC52150EBL1001), but also the abbreviation EBLXXXX (eg, study EBL1001) is used in this document.

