All participants will sign the informed consent form (ICF) and will be screened for eligibility at baseline (Day 1), which is also the day of Dose 1 vaccination. If needed, the screening activities may be split over multiple visits, with a maximum time of up to 28 days between signing the ICF and Dose 1 vaccination. Dose 2 vaccination will be given on Day 57. Participants in the immunogenicity subset and in Groups 5-6 will be followed for immunogenicity until the 21-day post Dose 2 visit (Day 78). Participants in Groups 5-6 will in addition be followed up from pre booster dose (Day 177) until 12 months after receiving the booster dose (Day 537). Samples for immunogenicity assessments will be taken pre Dose 1 (Day 1), pre Dose 2 (Day 57), 21 days post Dose 2 (Day 78), and in Groups 5-6 also pre booster dose (Day 177), and 7 days (Day 184), 21 days (Day 198), 6 months (Day 357), and 12 months (Day 537) after the booster dose. All participants will complete diary cards until 7 days post each vaccination (solicited adverse events), which will be reviewed by study site personnel at the Day 57 visit (before Dose 2 vaccination), at the Day 78 visit, and at the Day 184 visits (Groups 5-6 only). Unsolicited adverse events will be recorded until 28 days post each vaccination; participants will be asked about these at the Day 57 visit, at the Day 78 visit, at the Day 177, 184 and 198 visits (Groups 5-6 only), and by means of a telephone call at Days 29, 85, and at Day 205 (Groups 5-6 only). Serious adverse events will be recorded until the end of the study with a telephone call foreseen for Groups 1-4 only at 6 months post Dose 2 (Day 237).

The investigators, together with the sponsor's medical monitor, will be responsible for the safety monitoring of the study. If at least one pre-specified pausing rule is met, administration of study vaccine will be paused. According to the sponsor's standard procedures, a multidisciplinary Safety Management Team (SMT) is in place for the development of the Ebola vaccines regimen. This SMT will monitor the safety of the participants in this study as part of its regular surveillance of all clinical studies using the Ebola vaccines Ad26.ZEBOV, MVA-BN-Filo.

PARTICIPANT POPULATION

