Groups 1, 2, 3, 4, 5 and 6							
Study Procedures	Dose 1	28 days post Dose 1	Dose 2	21 days post Dose 2	28 days post Dose 2	6 months post Dose 2	
Screening/Administrative							
Informed consent ^{c,t}	X						
Inclusion/exclusion criteria	X ^d						
Medical history and demographics	X						
Prestudy-specific therapies ^e	X						
Randomization	X						
Prevaccination symptoms ^f	X ^g		X ^g				
Study vaccine administration	▲		▼				
Immunogenicity Assessments							
Blood sampling for immunogenicity assays (8.5 mL per blood draw) ^s (immunogenicity subset and Groups 5-6 only)	X ^g		X ^g	X			
Safety Assessments							
Urine pregnancy test ^h	X ^g		X ^g				
Physical examination ⁱ	X ^g		X ^g	X			
Vital signs ^j	X ^g		X ^g				
Distribution of participant diary ^k	X		X				
Review of participant diary by study site personnel ^l			X ^g	X			
30-minute postvaccination observation ^m	X		X				

	Screening/Baseline ^a	Vaccination and Postvaccination Visits ^b					Follow-up
		Day 1	Day 29 (Telephone call for safety follow-up) ±1w	Day 57 Groups 1-4: -3d, +28d (Day 54-85) ^u Groups 5 and 6: ±1w	Day 78 ±3d	Day 85 (Telephone call for safety follow-up) ±1w	
Groups 1, 2, 3, 4, 5 and 6							Day 237 ^r (Telephone call for safety follow-up) ±15d
Study Procedures	Dose 1	28 days post Dose 1	Dose 2	21 days post Dose 2	28 days post Dose 2		6 months post Dose 2
Solicited adverse events recording ⁿ	From Dose 1 vaccination until 7 days post Dose 1		From Dose 2 vaccination until 7 days post Dose 2				
Unsolicited adverse events recording ^{o,p}	From Dose 1 vaccination until 28 days post Dose 1		From Dose 2 vaccination until 28 days post Dose 2				
Pregnancy, serious adverse events ^o			Continuous				
Concomitant medications ^q	From Dose 1 vaccination until 28 days post Dose 1	From Dose 2 vaccination until 28 days post Dose 2				X ^q	

▲ Ad26.ZEBOV 5x10¹⁰ vp or placebo ▼ MVA-BN-Filo 1x10⁸ Inf U or placebo.

d: days; w: week

NOTE: If a participant withdraws early from the study, early withdrawal assessments should be obtained per the assessments for the 21-day post Dose 2 visit, with the exception of the immunogenicity assessments, if applicable. A participant who wishes to withdraw consent from participation in the study will be offered an optional visit for safety follow-up (before formal withdrawal of consent), but the participant has the right to refuse.

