2. OBJECTIVES, ENDPOINTS, AND HYPOTHESES

2.1. Objectives and Endpoints

Objectives	Endpoints
Primary	

 To demonstrate that the paired 2-dose vaccine regimens from 3 consecutively manufactured lots of Ad26.ZEBOV as Dose 1 and 3 consecutively manufactured lots of MVA-BN-Filo as Dose 2, administered at a 56-day interval, induce an equivalent humoral immune response. 	
 Binding antibody levels against the EBOV GP using enzyme-linked immunosorbent assay (ELISA, ELISA units/mL [EU/mL]) at 21 days post Dose 2 vaccination.
Secondary	

 To demonstrate that 3 consecutively manufactured lots of Ad26.ZEBOV as Dose 1 induce an equivalent humoral immune response. 	
 Binding antibody levels against the EBOV GP using ELISA (EU/mL) at 56 days post Dose 1 vaccination.

 To assess the safety and reactogenicity of a heterologous 2-dose vaccine regimen of Ad26.ZEBOV and MVA-BN-Filo administered IM on Days 1 and 57, respectively, using 3 different lots of 	
 Solicited local and systemic adverse events until 7 days post each vaccination. Unsolicited adverse events until 28 days post each vaccination.

Objectives	Endpoints
Ad26.ZEBOV and 3 different lots of MVA-BN-Filo.	
 • Serious adverse events until the end of the study.
Exploratory (Booster Cohort only)	

 • To assess the humoral immune response to a booster dose of Ad26.ZEBOV given 4 months after Dose 2. 	
 • Binding antibody levels against the EBOV GP using ELISA (EU/mL) at pre booster (Day 177) and several post booster timepoints (7-days, 21-days, 6-months and 12-months post booster dose).

 • To assess the safety and reactogenicity of a booster dose of Ad26.ZEBOV. 	
 • Solicited local and systemic adverse events until 7 days post booster vaccination. • Unsolicited adverse events until 28 days post booster vaccination. • Serious adverse events until the end of the study.

 • To assess the presence of neutralizing antibodies against the Ad26 vector. 	
 • Viral neutralizing antibody levels against the Ad26 vector at baseline, pre booster vaccination (Day 177), and at 21 days post booster vaccination.

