9. STUDY EVALUATIONS

9.1. Study Procedures

9.1.1. Overview

The [TIME AND EVENTS SCHEDULE](#) summarizes the frequency and timing of all measurements and evaluations applicable to this study.

Visit windows are provided in the [TIME AND EVENTS SCHEDULE](#). In case the Dose 2 or booster dose vaccination is postponed, the timing of the post Dose 2 and booster dose visits will be determined relative to the actual day of vaccination. The participant should be encouraged to come within these windows.

Additional urine pregnancy tests may be performed, as determined necessary by the investigator or required by local regulation, to establish the absence of pregnancy at any time during participation in the study.

The total blood volume to be collected from each participant in the immunogenicity subset will be approximately 25.5 mL. For the Booster Cohort, approximately 68 mL total blood volume will be collected (refer to Section 9.2).

Repeat or unscheduled samples may be taken for safety reasons or for technical issues with the samples.

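### The closing 28-day safety calls after Dose 2 and the booster may be made at day 21, so up to a week of unsolicited AE follow-up can rest on self-report or late recall

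*Protocol*

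**What the plan says.** Protocol section 2.1 makes "Unsolicited adverse events until 28 days post each vaccination" a secondary endpoint; the booster counterpart is exploratory. The Time and Events Schedule places the closing calls at "Day 85 (Telephone call for safety follow-up) ±1w" and, for Groups 5-6, "Day 205 (Telephone call for safety follow-up) ±1w", and labels them as 28 days after Dose 2 and after the booster. Under section 9.1.1, if Dose 2 or the booster is postponed, "the timing of the post Dose 2 and booster dose visits will be determined relative to the actual day of vaccination".

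The schedule's notes name the contacts at which participants are asked about unsolicited AEs. After Dose 2 (note p) these are "at the Day 78 visit, and by means of a telephone call at Days 29 and 85", where Day 29 belongs to Dose 1. For Groups 5-6 (note m) they are "at the Day 177 visit (before booster dose vaccination), Day 184 and Day 198 visits and by means of a telephone call at Day 205". Of the next contact in Groups 1-4, the Synopsis says: "Serious adverse events will be recorded until the end of the study with a telephone call foreseen for Groups 1-4 only at 6 months" after Dose 2 (Day 237). Section 9.1.2 describes that call more broadly, as one to assess safety, and gives the 6- and 12-month post-booster visits the purpose of long-term immunogenicity follow-up.

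In the SAP, Table 3 ends each post-dose period at 23:59 of day 28. Sections 5.1.1 and 5.1.2 tabulate participants with at least one AE in that period, section 5.1.3 assigns events by start date, and section 5.1.4 treats a participant who reports nothing as having no event.

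**The concern.** The analysis period is a fixed 28 days, but the contact that should close it may come a week early. After an early call, an event that starts before the end of day 28 reaches the database only if the participant volunteers it or recalls it months later. The SAP has no rule that marks such a participant as incompletely followed: the denominator stays the same and silence counts as no event.

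What is at stake is the accuracy of the descriptive 28-day rates of unsolicited AEs after Dose 2 (Groups 1-4) and after the booster (Groups 5-6). Enlarging the safety database is the stated reason in Protocol section 11.2 for raising each lot group from 144 to 234 participants.

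**Working it through.** **Inputs.** Dose 2 on Day 57, booster on Day 177, calls on Days 85 and 205 (±7 days), 21-day visits on Days 78 and 198 (±3 days), next contacts on Days 237 and 357 (all Time and Events Schedule); analysis period to the end of day 28 (SAP Table 3); planned group sizes 234 and 50 (Protocol Table 1).

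**1. The plan's own labels.** 85 − 57 = 28 and 205 − 177 = 28. Both reproduce.

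**2. Earliest call.** 85 − 7 − 57 = 21 and 205 − 7 − 177 = 21. In-window calls span days 21 to 35 after the dose. If the dose is late, the call moves with it.

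**3. Longest unasked stretch.** 28 − 21 = 7 days. The 21-day visit falls on days 18 to 24; at its latest it cuts the gap to 28 − 24 = 4 days.

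**4. Time to the next contact from the earliest call.** 237 − 78 = 159 days and 357 − 198 = 159 days, about five months. The primary analysis locks once Groups 1-4 have reached the 28-day time point, and the booster interim analysis locks likewise, so recollection at the next contact would generally come too late for those tables.

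**5. Which doses are exposed.** Dose 1 is asked about again at Day 57, and Dose 2 in Groups 5-6 again at Day 177, for those who attend. A participant who never returns for Dose 2 has the Day 29 call as the last listed enquiry. That call has the same ±1 week window, so it too may come at 29 − 7 − 1 = 21 days.

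**6. Size, under assumptions.** The documents give no call dates, onset times, AE incidence or self-report rates. Assume no self-report and a true 28-day any-AE incidence I. With constant hazard, a participant last asked on day d shows an event with probability 1 − (1 − I)^(min(d,28)/28). With front-loaded onset, the exponent becomes (1 − e^(−min(d,28)/10)) / (1 − e^(−2.8)). Averaging over call days:

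| Onset | Call days | I = 10% | I = 20% | I = 40% |
|---|---|---|---|---|
| Constant | Uniform, 21-35 | 9.4% | 18.8% | 37.9% |
| Constant | Uniform, 25-31 | – | 19.4% | – |
| Front-loaded | Uniform, 21-35 | 9.9% | 19.7% | 39.5% |
| Front-loaded | All at day 21 | 9.4% | 18.8% | 38.0% |
| Constant | All at day 21 (extreme) | 7.6% | 15.4% | 31.8% |

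With calls uniform over days 21 to 35, the mean unasked time is (7+6+5+4+3+2+1)/15 = 1.9 days. At I = 20%, the first row loses 1.2 points: 0.0121 × 234 = 2.8 participants, or 0.0121 × 50 = 0.6. The sampling standard errors are √(0.2×0.8/234) = 2.6 points and √(0.2×0.8/50) = 5.7 points. Any self-report makes every loss smaller.

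**The case against.** The case for leaving the window alone is that ±1 week is a scheduling tolerance and does not shorten the 28-day recording obligation. Several safeguards remain. Participants are told to contact the investigator about "any adverse event or intercurrent illness that they perceive as relevant and/or can be possibly related to study vaccine in their opinion". Protocol section 9.3.1 requires clinically relevant changes during the study to be recorded. Section 12 prefers open-ended questioning, and section 9.1.2 describes the Day 237 call as a general safety call. Late reports enter the tables by start date. Safety is descriptive only, and a later call lengthens recall.

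Most of this stands and limits the point. Collection after an early call is passive, not absent, and a reader who infers that nothing is collected, or that Day 237 is strictly for serious AEs, goes beyond the documents. The safeguards do not close the gap, though. The self-report instruction covers what the participant judges relevant or related, whereas the endpoint is all unsolicited AEs. Day 237 is about five months away and is not among the contacts listed for this enquiry.

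Two further inferences are tempting. One is that the loss is probably about one percentage point. That needs 20% incidence, uniform calls, constant hazard and no self-report together; other plausible cases in the table give 0.3 to 0.6 points. The other is that the error can only be downward. SAP Attachment 2 lets an AE with a partial date be assigned to more than one period, so an event after day 28, recalled late with only month and year, could enter the 28-day table. Downward is the expected direction, not a certainty.

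**Conclusion.** The point holds as a minor design weakness. The window arithmetic and the list of contacts are fixed by the documents: up to 7 of 28 days may go without active enquiry after Dose 2 in Groups 1-4 and after the booster in Groups 5-6, and after Dose 1 in participants who never return. The effect on the rates is not fixed. At an assumed true 20% it is roughly 0 to 1.2 points, below the sampling error of a single group. The 4.6-point loss in the extreme row (20% − 15.4%) needs every participant last asked at day 21, constant onset and no self-report, and should not be read as an expectation.

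A reader might infer a threat to the lot comparison. The documents do not support that: the window is the same in every group, contacts are made under blinding, and the equivalence tests use antibody concentrations. Power is untouched, and serious AEs are collected to the end of the study.

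**What to change.** Make the Day 85 and Day 205 call windows one-sided, counted from the actual vaccination day: 0/+1 week (Days 85-92 and 205-212) or 0/+2 weeks (Days 85-99 and 205-219). The second keeps the present 14-day width. Both keep Days 85 and 205, which the protocol names in many places, and leave only the rest of day 28 uncovered. Starting at day 29 would close that remainder but would exclude the nominal days and contradict the text elsewhere. Use the same one-sided window for future Day 29 calls in the Booster Cohort, for participants who do not return for Dose 2. In the SAP, add a listing of participants whose last AE enquiry came before day 28, including Groups 1-4 calls already made.

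The cost is a protocol amendment, one listing and slightly longer recall; no contact is added. The mid-window call moves from day 28 to day 31.5 (0/+1 week) or day 35 (0/+2 weeks). The latest in-window call stays at day 35 with 0/+1 week, at the price of possibly more out-of-window calls. With 0/+2 weeks it moves to day 42, so the 28-day data cut could come up to one week later. The gain is mainly for the Booster Cohort, not yet recruited at Amendment 3, and for Groups 1-4 participants not yet called.
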